### Potential pantoprazole effect on premature discontinuation of antithrombotic treatment

A time-to-event variable “Time to premature discontinuation of rivaroxaban/aspirin study treatment” will be defined as follows:

For those subjects with documentation of premature discontinuation of either rivaroxaban/placebo or aspirin/placebo treatment before the common outcomes cut-off date used in CDB1, February 06, 2017, time (in days) from randomization to the occurrence of the event will be derived as:

- the date of permanent treatment discontinuation – the randomization date + 1.

This will constitute an uncensored observation.

For those subjects without documentation of premature discontinuation of either rivaroxaban/placebo or aspirin/placebo treatment before the common outcomes cut-off date used in CDB1, February 06, 2017, time (in days) from randomization to the censoring date will be derived as:

- common outcomes cut-off date – the randomization date + 1.

This will constitute a right-censored observation.

A potential effect of pantoprazole treatment on premature discontinuation of antithrombotic treatment will be analyzed in the pantoprazole ITT analysis set using a log-rank test and a Cox proportional hazards model.

In the unlikely event that the risk to prematurely discontinue antithrombotic treatment is significantly reduced in the pantoprazole treatment group, further analyses will be performed to explore this finding. This exploration may include a time-dependent Cox model investigating the effect of premature discontinuation of antithrombotic treatment on major cardiovascular outcomes.

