### **Censoring rules for secondary safety analyses related to the rivaroxaban/aspirin randomization**

- For secondary safety analyses based on the safety analysis set and the ITT data scope, all randomized subjects with at least one dose of either randomized study medication and without documentation of an outcome event within the ITT data scope will be censored as stated above for study rivaroxaban/aspirin analyses according to the ITT principle.
- For "treatment-emergent" secondary safety analyses, all randomized subjects with at least one dose of study medication and without documentation of an outcome event within the

 Text modified as per modification 1 in integrated SAP, Version 3.0.

 Text modified as per modification 1 in integrated SAP, Version 3.0.

 Text modified as per modification 1 in integrated SAP, Version 3.0.

“treatment-emergent” data scope will be censored at the date of last double-blind dose of antithrombotic study treatment + 2 days.

Note that if a subject stops treatment at the Final rivaroxaban/aspirin Follow-up Visit and experiences an event up to 2 days thereafter, the event will be counted in this analysis but not in the primary analysis using the ITT data scope.

- For secondary safety analyses based on the safety analysis set and the “plus 30 days safety” data scope, all randomized subjects with at least one dose of study medication and without documentation of an outcome event within the “plus 30 days safety” data scope will be censored at the date of last double-blind dose of antithrombotic study treatment + 30 days.

Note that if a subject stops treatment at the Final rivaroxaban/aspirin Follow-up Visit and experiences an event up to 30 days thereafter, the event will be counted in this analysis but not in the primary analysis using the ITT data scope.

- For secondary safety analyses based on the safety analysis set and the “Study rivaroxaban/aspirin Follow up + Wash out” data scope, all randomized subjects with at least one dose of study medication and without documentation of an outcome event will be censored at the subject’s last contact date during the rivaroxaban/aspirin portion of the study.

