## 2. Study Objectives

The main objective for the pantoprazole randomization is

- To determine whether pantoprazole 40 mg od compared with placebo reduces the risk of upper gastrointestinal bleeding, ulceration, or gastrointestinal obstruction or perforation in subjects with CAD or PAD receiving antithrombotic medications.

Other objectives for the pantoprazole randomization are:

- To determine the effect of pantoprazole 40 mg od compared with placebo on the risk of pneumonia, clostridium difficile (C. diff) and other enteric infections, bone fractures, and new diagnosis since randomization of gastric atrophy, chronic kidney disease, diabetes, chronic obstructive lung disease and dementia in subjects with CAD or PAD.
- To determine whether treatment with pantoprazole 40 mg od potentially modifies the effects of antithrombotic treatment on major cardiovascular outcomes or bleeding events. I.e. whether pantoprazole interacts with the treatment effects of rivaroxaban 2.5 mg bid/aspirin 100 mg od vs. aspirin 100 mg od in its impact on outcomes.
- To determine whether treatment with pantoprazole 40 mg od has an effect on premature discontinuation of antithrombotic study treatment.

For further details on study objectives, please refer to integrated [SAP](#), version 4.1.

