### 4.2.3 Pantoprazole treatment emergent data scope

The pantoprazole treatment emergent data scope includes outcome events from randomization up until two days after permanent discontinuation of pantoprazole study treatment.

It will be used for secondary safety analyses in the pantoprazole safety analysis set. All subjects randomized to pantoprazole/placebo with at least one dose of pantoprazole/placebo study medication and without documentation of an outcome event within the pantoprazole treatment-emergent data scope will be censored at the date of last dose of pantoprazole study treatment + 2 days.

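### PPI SAP 5.1.3 censors time to antithrombotic discontinuation at 6 February 2017 even for subjects lost, withdrawn or dead before then: a minor, easily corrected conflict with the plan's other censoring rules

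*SAP*

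**What the plan says.** PPI SAP Section 2 lists among its other, not main, objectives: "To determine whether treatment with pantoprazole 40 mg od has an effect on premature discontinuation of antithrombotic study treatment". Section 5.1.3 defines the variable.

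- **Events:** "For those subjects with documentation of premature discontinuation of either rivaroxaban/placebo or aspirin/placebo treatment before the common outcomes cut-off date" (6 February 2017). The time runs from randomization to permanent discontinuation.
- **Censored:** "For those subjects without documentation of premature discontinuation of either rivaroxaban/placebo or aspirin/placebo treatment before the common outcomes cut-off date". The time is "common outcomes cut-off date – the randomization date + 1", and the plan calls it a right-censored observation.
- **Analysis:** the effect "will be analyzed in the pantoprazole ITT analysis set using a log-rank test and a Cox proportional hazards model".

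The censoring rule makes no exception for death, withdrawal of consent or loss to follow-up, and no general rule elsewhere in the PPI SAP overrides it.

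**The concern.** A subject lost in 2015 with no discontinuation recorded stays in the risk set as still taking study drug until February 2017, although nobody knows whether that is so. A subject who died on drug in 2015 is also counted as at risk for the rest of the period.

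An ordinary right-censored log-rank or Cox analysis assumes that each subject at risk is under observation and able to have the event. If that fails, cumulative discontinuation is pulled down. If death or loss differs between pantoprazole and placebo, some of that difference passes into the hazard ratio. A programmer also meets conflicting definitions and has to choose one.

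**Working it through.** **1. The rules side by side.**

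| Place | Where a subject without the event stops | Stops at loss or death? |
|---|---|---|
| SAP 4.1, Section 4.5.3, rivaroxaban/aspirin ITT rule | Earlier of 6 February 2017 and last contact; Section 4.5.1 sets last contact to the death date | Yes |
| PPI SAP 4.2.1, ITT scope | The subject's own Last Follow-up Date, defined in Section 6 | Yes |
| PPI SAP 5.1.3, discontinuation variable | 6 February 2017 | No |

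SAP 4.1 Table 10-2, written for the missing-data sensitivity analyses, adds two relevant classifications. Follow-up non-completers count as study treatment non-completers, whereas PPI SAP 5.1.3 holds the same subject at risk as still treated if no stop is documented. A subject whose last dose date equals the death date counts as a treatment completer. Read that way, a death on drug is not a discontinuation and falls under the late-censoring rule.

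**2. Size.** The plan states no figure for this analysis, so there is none to reproduce. Inputs:

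- Discontinuation of 6%, 4.5%, then 3% per six months (SAP 4.1, Section 7).
- Death or loss of 1-3% per year. This is an assumption: Section 7 gives only non-CV death of almost 1% per year.
- Follow-up to the cut-off uniform over 0.9-2.9 or 0.9-3.9 years (assumption).
- No subject who died or was lost carries a recorded stop (assumption, and the worst case).

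If nobody died or was lost, two-year discontinuation would be 1 − 0.94 × 0.955 × 0.97² = 15.5%. At three years it would be 1 − 0.94 × 0.955 × 0.97⁴ = 20.5%.

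A simulation with 400,000 subjects per arm compared the plan's rule with censoring at the earlier of cut-off and death or loss (equal rates in both arms, no pantoprazole effect):

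| Follow-up, death or loss per year | Subjects affected | Share of at-risk time | 2 years: earlier date / plan | 2.8 years: earlier date / plan |
|---|---|---|---|---|
| 0.9-2.9 y, 1% | 1.7% | 1.1% | 15.4 / 15.3% | 19.5 / 19.3% |
| 0.9-2.9 y, 3% | 5.0% | 3.1% | 15.4 / 15.0% | 19.5 / 18.9% |
| 0.9-3.9 y, 1% | 2.1% | 1.4% | 15.6 / 15.5% | 19.6 / 19.4% |
| 0.9-3.9 y, 3% | 6.1% | 4.1% | 15.6 / 15.2% | 19.7 / 19.0% |

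The gap is 0.1-0.4 percentage points at two years and 0.2-0.7 at 2.8 years.

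**3. Hazard ratio.** With equal death or loss in the two arms, the two rules differ by less than 0.001 (for example 0.9947 against 0.9945 at 2% per year). With a 20% relative difference they differ by 0.003-0.007. The largest shift was 0.9919 to 0.9986, a difference of 0.0067, at 3.0% against 2.4% per year. The arm with more death or loss appears to discontinue less.

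**4. Deaths alone.** With follow-up of 0.6-3.9 years and all exits treated as deaths at 1.5, 2 and 3% per year, the plan's rule gives three-year discontinuation of 20.2, 20.0 and 19.7%. The true cumulative incidence with death as a competing event is 20.2, 20.0 and 19.8%. They agree to within 0.1 points. The 20.5% above answers a different question: the risk if nobody died.

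**The case against.** The strongest defence concerns deaths. The administrative cut-off is known for everyone, so keeping a subject who died on drug at risk until that date is the subdistribution risk set, and step 4 shows that it returns the competing-risk incidence. A reader might infer that the reported discontinuation rates are simply understated. For deaths the documents do not support that, because the lower figure is a legitimate quantity. What stands is that the plan names no such estimand and presents ordinary right-censoring with a log-rank test and a Cox model. The defence does not extend to subjects lost or withdrawn, whose later treatment status is unknown.

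That remaining group may be small. SAP 4.1 Section 4.2 defines premature discontinuation as stopping for any reason and expects very few subjects with incomplete follow-up. A lost subject with a discontinuation report is an event, not a late censoring. How many lack a report depends on form-filling practice that the documents do not show.

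Two wider readings are also tempting.

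- The safety scopes, where subjects "will be censored at the date of last double-blind dose of antithrombotic study treatment + 30 days" or "will be censored at the date of last dose of pantoprazole study treatment + 2 days", likewise name no cap at death or last contact. The excess, however, cannot pass 30 or 2 days per subject. Even with 6.2% of subjects affected and a mean of 2.4 years (877 days) to the cut-off, it is about 0.062 × 30 / 877 = 0.2%, or 0.062 × 2 / 877 = 0.01%. That is negligible.
- Section 5.1.3 mentions no stratification by antithrombotic arm, unlike the main pantoprazole comparison in Section 5.2.3. The antithrombotic randomization was itself stratified by pantoprazole allocation (SAP 4.1, Section 3), so an unstratified test is valid. This is a matter of consistency, not an error.

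**Conclusion.** The concern holds in a limited form. The censoring rule in PPI SAP 5.1.3 departs from SAP 4.1 and from the PPI SAP's own ITT scope. It treats subjects lost or withdrawn without a recorded stop as known to be on drug, which is an error. For deaths it leaves the estimand unnamed, which is a gap in specification.

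Under the stated assumptions about 2-6% of subjects and 1-4% of at-risk time are affected. These are upper figures, because they pool death with loss and suppose that none has a recorded stop. Of the 0.1-0.7 point difference in cumulative discontinuation, only the part due to loss or withdrawal is error. The documents give no loss rate from which to separate it.

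A reader might infer that the pantoprazole comparison is invalid. The figures do not support that: the hazard ratio is almost unchanged unless death or loss differs by arm, and it moves by less than 0.01 even with a 20% relative difference. Severity is minor. This is an other objective, and Section 5.1.3 would follow a significant reduction only with further exploration.

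**What to change.** In PPI SAP 5.1.3, censor subjects without a documented discontinuation at the earlier of 6 February 2017 and the Last rivaroxaban/aspirin Follow-up Date, which Section 6 already defines and which stops at death. Use this for the log-rank test and describe the Cox model as cause-specific. Show cumulative discontinuation with death on treatment as a competing event. The two serve different purposes and will give slightly different figures, so the text should say which is which.

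State also whether a death on treatment, a loss or a withdrawal counts as a discontinuation, consistently with SAP 4.1 Section 4.2 and Table 10-2. For withdrawn consent this matters because the Section 6 date can be a later date at which only survival was confirmed.

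The cost is a few lines of text and minor reprogramming. No documented discontinuation is lost and no new data are needed.

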### **5.1.4 Protocol Deviations**

No per protocol analysis set will be defined in this study. The number of subjects with major protocol deviations according to the CRF will be summarized by randomized pantoprazole and antithrombotic treatment groups, and overall. The types of deviations are described in the Data Management Plan.

### **5.1.5 Medical History**

Medical history will be evaluated by frequency tables in the ITT analysis set (and, for CSR purposes, the pantoprazole safety set) by pantoprazole treatment groups, showing the number of subjects with medical history findings (i.e., listed conditions of previous diagnoses, diseases, or surgeries based on the CRF).

### **5.1.6 Demographics**

Demographic data will be evaluated descriptively for the ITT analysis set (and, for CSR purposes, the pantoprazole safety set) by PPI and antithrombotic study treatment groups, and overall.

Descriptive statistics (such as mean, standard deviation, median, quartiles, minimum and maximum) will be provided for continuous variables such as

- Age [years]
- Height [cm]
- Weight [kg]
- Waist and hip circumference [cm]
- Body mass index [kg/m^2]

Counts and (appropriate) percentages will be provided for categorical variables such as

- Gender
- Ethnic group and ethnicity/race
- Tobacco use

### **5.1.7 Prior and Concomitant Medication**

Frequency tables by pantoprazole treatment group and overall, will be used to summarize the number of subjects with

- prior relevant antiplatelet agents and anticoagulant reported by the subject at the Screening/Run-in Visit
- relevant concomitant medications at randomization (non-study medications taken regularly for at least 1 month at the time of the randomization visit), for CDB2 defined as: non-study proton pump inhibitor and Non-steroidal anti-inflammatory drugs (NSAIDs).
- non-study antithrombotic therapy (antiplatelet agents and anticoagulant) reported at the scheduled follow-up visits
- relevant concomitant medications recorded at a Follow-Up Visit 2 years after randomization
- relevant concomitant medications recorded at the Final Follow-Up Visit(s).

### 5.2 Efficacy

In general, due to the early discontinuation of antithrombotic treatment arms, subjects randomized to pantoprazole 40 mg or placebo on the one hand and subjects not randomized to pantoprazole/placebo but randomized to antithrombotic treatment only on the other hand, are suspected to differ in time under observation systematically. The following analyses attempt to take this bias into account.

#### 5.2.1 Efficacy Variables for the Pantoprazole Randomization

The main efficacy variable for the pantoprazole randomization is the time (in days) from randomization to the first occurrence of an unrefuted GI outcome event, which is the composite of the following outcomes:

- Overt bleeding of gastroduodenal origin confirmed by endoscopy or radiography
- Overt upper gastrointestinal bleeding of unknown origin
- Bleeding of presumed occult upper gastrointestinal tract origin with documented decrease in Hb of 2 g/dL
- Symptomatic gastroduodenal ulcer
- Gastrointestinal pain with underlying multiple gastroduodenal erosions
- Upper GI obstruction/perforation.

Details by individual components will also be presented.

Further outcomes of interest for the pantoprazole randomization, which will also be evaluated as time-to-event variables, are:

- GI bleeding, defined as the composite of the first three components above:
  - Overt bleeding of gastroduodenal origin confirmed by endoscopy or radiography
  - Overt upper gastrointestinal bleeding of unknown origin

- Bleeding of presumed occult upper gastrointestinal tract origin with documented decrease in Hb of 2 g/dL

### 5.2.2 Efficacy Outcomes for the Antithrombotic Randomization by Pantoprazole Treatment Groups

Other efficacy outcomes of interest are the unrefuted occurrences of outcomes which had been defined in the clinical study protocol for the objectives of the antithrombotic randomization, i.e.:

- MI, stroke, or CV death
  - MI
  - Stroke
  - CV death (and its cause)
- MI, ischemic stroke, ALI, CHD death
  - Ischemic Stroke
  - ALI
  - CHD death
- MI, ischemic stroke, ALI, CV death
- All-cause mortality
  - Non-CV death (and its cause)
- Major adverse limb event
  - ALI
  - Chronic limb ischemia
- New diagnosis of cancer (including subtypes)
- Recurrence of cancer
- Hospitalization
  - Hospitalization for CV reasons

Other outcomes of interest for the antithrombotic randomization related to cognition and function will be reported separately.

### 5.2.3 Statistical Analysis for the Pantoprazole Randomization

The following analyses are to be conducted for the efficacy variables of the pantoprazole randomization as defined in section 5.2.1 separately for the ITT data scope for CDB2

- in the pantoprazole ITT analysis set and
- in the subjects not randomized to pantoprazole/placebo.

#### Descriptive statistics for pantoprazole outcomes

For outcomes relevant for the pantoprazole/placebo randomization, the number of subjects with event, crude incidences and incidence rates will be depicted in the following manner:

Subjects randomized to pantoprazole 40 mg or placebo on the one hand and subjects not randomized to pantoprazole/placebo on the other hand are suspected to differ in time under observation systematically. Hence, those two groups will be displayed in separate tables to avoid potential confusion arising from erroneously comparing these groups, see the following example:

The following tables will be repeated for the antithrombotic treatment arms <xxx>:

- Overall and,
- for CSR purposes only, by antithrombotic treatment arm
  - Randomized to Rivaroxaban 2.5 mg bid, Aspirin 100 mg od
  - Randomized to Rivaroxaban 5 mg
  - Randomized to Aspirin 100 mg od

**Table: Number of subjects with <event> in ITT data scope for CDB2 (pantoprazole ITT analysis set)**

	Pantoprazole 40 mg od N=xxx (100%)		Pantoprazole placebo od N=xxx (100%)		Total N= xxx (100%)	
	N (%)	N/100 p-yrs (95% CI)	N (%)	N/100 p-yrs (95% CI)	N (%)	N/100 p-yrs (95% CI)
<event>	xx ( x.x%)	x.xx (x.xx;x.xx)	xx ( x.x%)	x.xx (x.xx;x.xx)	xx ( x.x%)	x.xx (x.xx;x.xx)
- Only events that occurred during ITT data scope for CDB2 are taken into account.						

**Table: Number of subjects with <event> in ITT data scope for CDB2 (ITT analysis set)**

	Not randomized to pantoprazole/placebo N=xxx (100%)	
	N (%)	N/100 p-yrs (95% CI)
<event>	xx ( x.x%)	x.xx (x.xx;x.xx)
- Only events that occurred during ITT data scope for CDB2 are taken into account.		

**Inferential statistics for pantoprazole outcomes**

The statistical analysis of the outcome for the pantoprazole randomization will be based on the intention-to-treat principle and will include all subjects randomized to receive pantoprazole 40 mg od or pantoprazole placebo.

The null hypothesis  $H_{0;panto40}$  stating that

“there is no difference between the pantoprazole treatment and control group in the probability of the outcome for all time points”

will be tested against the alternative hypothesis  $H_{1;panto40}$  stating that

“there is a difference between the two groups in the probability of the outcome for at least one time point”.

**Stratified log-rank test and Kaplan-Meier estimates**

Statistical testing will be performed by a comparison of the “survival functions”  $S(t)$ , i.e., the probability that “time from randomization to the first occurrence of the outcome” is  $> t$ , for a time  $t$  relative to randomization. The comparison will be performed using a log-rank test stratified by antithrombotic study treatment (three strata levels: rivaroxaban 2.5 mg bid + aspirin 100 mg od; rivaroxaban 5 mg bid + aspirin placebo; rivaroxaban placebo + aspirin 100 mg od), conducted at the 2-sided 5% type I error level.

Kaplan-Meier estimates of cumulative risk functions and Nelson-Aalen estimates of the cumulative hazard functions will be provided to evaluate the timing of event occurrence in the two proton pump inhibitor study groups and the consistency of the treatment effect for all time points (the two survival curves do not cross).

To derive the log-rank Z test statistic and the variance V of the log-rank statistics, SAS program code corresponding to the following will be used:

```
PROC LIFETEST DATA = <dataset> ALPHA = 0.05 METHOD = KM NELSON;
STRATA stratumn / GROUP = ppilgrp TEST = (LOGRANK);
TIME ttevalue * ttecnsr(1);
RUN;

/*
where
dataset = name of sub-dataset including all ITT subjects randomized to pantoprazole
          treatment groups: pantoprazole 40 mg/pantoprazole placebo
ppilgrp = variable coding randomized pantoprazole treatment group (0 = pantoprazole
          placebo, 1 = pantoprazole 40 mg)
ttevalue = time to first occurrence of pantoprazole outcome event
ttecnsr = censoring index (1 = right-censored, 0 = event)
stratumn = variable for antithrombotic stratification factor (three levels)
*/
```

### Cox proportional hazards model

Hazard ratios and corresponding 2-sided 95% confidence intervals will be estimated based on a Cox proportional hazards model stratified by antithrombotic therapy study group. Censoring will be assumed independent of the treatment group assignment.

For the analysis of the outcome for the pantoprazole randomization in this study, the hazard function  $h(t)$  is the chance that an individual experiences an event of the outcome of the pantoprazole randomization in the next instant in time, given that the individual has not had such an event up to time  $t$ . For example, for the comparison of pantoprazole 40 mg od to pantoprazole placebo (control), the corresponding stratified Cox proportional hazards model can be described by the following equation:

$$h_k(t, x_i) = h_{0k}(t) \exp(\beta x_i),$$

where

- $h_k(\cdot)$  hazard function for primary efficacy outcome for stratum  $k$ ,  $k = 1, 2, 3$  ( $k$  represents randomized antithrombotic study treatment stratification factor), as a function of time and subject’s covariates
- $h_{0k}(\cdot)$  unspecified underlying baseline hazard function for primary efficacy outcome per stratum  $k$ ; hazard of an individual with  $x_i = 0$

- t time (in days) relative to the randomization date
- $x_i$  PPI treatment group of subject  $i$   
(0 corresponds to “pantoprazole placebo (control)” and  
1 corresponds to “pantoprazole 40 mg od”)
- $\beta$  unknown parameter (to be estimated); hazard ratio =  $\exp(\beta)$

SAS program code corresponding to the following will be used:

```

PROC PHREG DATA = <dataset>;
  MODEL ttevalue * ttecnsr(1) = ppilgrpn / RL TIES=EFRON ALPHA=0.05;
  STRATA stratumn;
RUN;

/*
where
dataset = name of sub-dataset including all ITT subjects randomized to
          pantoprazole 40 mg or pantoprazole placebo study treatment
ppilgrpn = variable coding randomized pantoprazole treatment group
          (0 = pantoprazole placebo, 1 = pantoprazole 40 mg treatment)
ttevalue = time to first occurrence of pantoprazole outcome event
ttecnsr = censoring index (1 = right-censored, 0 = event)
stratumn = variable for randomized antithrombotic study treatment
          stratification factor (three levels)
*/

```

Additional procedure options controlling the output may be added to the program codes.

